4.2. Required Behavior

If the participant is prescribed antibiotics or any other medications for any reason, they should report this prescription and they will be withdrawn from the trial as of the prescription date.

Participants are asked not to ingest or take any other form of cold remedy (over-the-counter (NyQuil/Dayquil/Cough Syrup/Cough Drops/EmergenC/Airborne/Zarbee's or any similar cold-relief product or prescription drugs) during the 18-day study period. If taken during the study duration the participant will record this as part of their diary and will be exited from the study.

Because none of the active ingredients are aimed at pain relief or reducing fever, participants will be allowed to take pain relievers/fever reducers (Advil/Tylenol or their equivalent).

Participants are asked to limit the consumption of alcohol beverages to less than or equal to two drinks per day and avoid recreational drugs or use of cannabis during the study period.

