4.3. Participation Period

Participants are expected to participate in the study for 18 days after the onset of the first cold. Onset is defined as the day that the participant experiences 2 or more cold symptoms. Participant will be exited once all symptoms have been resolved or at 18 days whichever is shorter. If no cold has started within 90 days of participant study start date (date the participant receives and records receipt of test product) participants will be exited from the study.

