- Participant will take the test product twice a day, at least 4-6 hours apart.
- The next day the participant will complete their symptom diary prior to taking the test product. Once completed they will mix 1 packet of the test product into 6-8 oz of water and consume the whole drink. They will take the test product again 4-6 hours later.
- The participant will complete this process daily until their cold symptoms resolve or for 18 days, whichever is shorter.
- If the participant takes ibuprofen or acetaminophen at any time, the participant will record this on their symptom diary.
- After taking the test product, the participant will be instructed to fill out an Adverse Event form for any side-effects experienced.
- The participant will be prompted, by email, to complete the study exit form once the participant's symptoms resolve completely or after 18 days, whichever is shorter.
- Neither the sponsor nor Hawthorne Effect, Inc. will make any attempt to collect any unused test product.
- Upon receipt of study exit survey and review of completed study forms, participant will receive an Amazon gift card of \$25 via email.

6.2.Study Schedule of Activities

Assessments	Screening	Consent	Before Receipt of Test Product	Product Received	Event Start Date**	Days 1-18*	Study Exit***
Study Window							
Screening Survey	Х						
Consent		Х					
Baseline Survey			х				
Demographics			х				
Acknowledgement of Receipt of Test Product				Х			
Test Product Consumed****					Х	Х	
Symptom Diary					Х	Х	Х
Meds & Supplements			Х				
AE Assessment					Х	Х	Х
Study Exit Survey							Х

^{*}Participant will participate in the study starting on the day of the cold until the cold symptoms resolve or 18 days whichever is shorter.

^{**} The day the participant experiences 2 or more of the protocol defined symptoms

^{***} The participant will exit the study at the time of complete cold symptom resolution, 18 days after the start of cold symptoms, or at 90 days if no cold is experienced by the participant.

^{****} The product will be consumed twice a day, 4-6 hours apart

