6.4. Adverse Event and Safety Monitoring

Adverse Events (AEs) are defined as any untoward medical occurrences described by the study participant. All AEs will be self-reported and documented on the platform. The AEs will be reviewed by the study team including the remote trial coordinator and study principal investigator and reported according to the IRB requirements. Participants who experience adverse events will be advised to stop taking the test product and seek medical attention.

In the event that a participant experiences an adverse event, the clinical study manager or clinical ops coordinator will notify both the PI and Sponsor. The Sponsor will take appropriate action according to their standard operating procedures for any adverse events that warrant action by the sponsor.

6.4.1.Anticipated Adverse Events

Anticipated Adverse Events are complications that are known to be associated with the test product (in high doses exceeding recommended use):

- epigastric pain
- nausea
- vomiting
- loss of appetite
- abdominal cramps
- diarrhea
- headaches

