6.4.3. Serious Adverse Events

A Serious Adverse Event is an Adverse Event that leads to death or to serious deterioration in the health of the participant that either resulted in a life-threatening illness or injury, or a permanent impairment of a body structure or body function.

6.5.Lost to Follow-Up

If a participant fails to provide event information via the study/patient portal 30 days after the start of the trial, the remote coordinator will attempt to contact the participant to ascertain whether or not the participant has had a cold or not and if the participant wishes to and/or should continue in the study.

Before a participant is deemed lost to follow up, the investigator or designee must make every effort to regain contact with the participant (where possible, 3 telephone calls and, if necessary, a certified letter to the participant's last known mailing address or local equivalent methods). These contact attempts should be documented in the participant's study record.

Should the participant continue to be unreachable, he/she will be considered to have withdrawn from the study and the study exit form will be completed.

6.6.Test Product Packaging/Handling/Storage/Accountability

- The 18-day supply of test product (36 packets) will be packaged and labeled with a study ID number.
- Participants will receive guidance on how to report receipt, store, and use the test product.
- Hawthorne Effect Inc. will support storage and shipment of test product, documentation of test product assignment, and completion of test product accountability.

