13.1.7. Appendix G Adverse Event Form

Immune AE document

- 1. Did you experience any side effects after taking the test product? Y/N
 - a. If so, did you experience any of the following
 - o itching, rash, hives, throat/lip/tongue swelling, wheezing
 - low blood pressure, fainting, chest pain, shortness of breath, palpitations, irregular heart beat
 - o severe, persistent nausea, vomiting, diarrhea, or abdominal pain
 - o difficulty urinating, decreased urination
 - o fatigue, appetite loss, yellowing skin/eyes, itching, dark urine
 - severe joint/muscle pain
 - o slurred speech, one-sided weakness of face, arm, leg, vision
 - o abnormal bleeding from nose or gums
 - o blood in urine, stool, vomit,
 - o marked mood, cognitive, or behavioral changes, thoughts of suicide
 - o Other:
- 2. Please give a description of the event
- 3. How soon after taking the test product did you experience the side effect?
- 4. What did you do to alleviate the side effect?
- 5. Did you have to go to the hospital or see a doctor for this side effect?
 - a. Please describe any diagnosis or treatment that they provided.
 - b. If you were seen in the hospital, please upload any discharge paperwork or other documents from the hospital.

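### Adverse event assessment is scheduled only up to study exit, so late-onset events and the outcomes of events that lead to a prescription are not systematically collected

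*Combined protocol and SAP*

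**What the plan says.** **End of participation.** Section 4.3 states: "Participant will be exited once all symptoms have been resolved or at 18 days whichever is shorter". The footnote to the schedule in Section 6.2 agrees: "The participant will exit the study at the time of complete cold symptom resolution, 18 days after the start of cold symptoms", or 90 days where no cold occurs.

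**AE collection.** The schedule row labelled "AE Assessment" is marked at the event start date, on Days 1-18 and at study exit. No column follows study exit. The daily diary (Appendix E, item 12) asks about side effects and directs the participant to the AE form.

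**Action on an AE.** Section 6.4: "Participants who experience adverse events will be advised to stop taking the test product and seek medical attention". Section 2.2.3 adds that such participants may leave the study.

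**Action on a prescription.** Section 4.2: "If the participant is prescribed antibiotics or any other medications for any reason", then "they should report this prescription and they will be withdrawn from the trial as of the prescription date".

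**What is recorded.** Section 6.4.2 has the investigator rate relatedness, severity and causality. Appendix G asks for a description, the time to onset, what was done, and any diagnosis or treatment; for hospital care it adds "please upload any discharge paperwork or other documents from the hospital". Neither place asks for a stop date or an outcome.

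**Use.** A summary of AEs is a secondary endpoint in the synopsis and in Sections 3, 7.1 and 7.3.

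**The concern.** The end of efficacy follow-up also serves as the end of safety follow-up. For the primary endpoint, stopping at resolution or day 18 is sensible. For safety it means that a participant who recovers can leave within about a day of the last packets, with no later contact planned.

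Sections 6.4 and 4.2 also work against each other for data collection. One sends participants with an AE to seek medical care. The other ends participation on the day that care produces a prescription. The AEs with the most to follow are then the ones whose planned follow-up can end earliest.

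The plan itself needs some of the missing information. Its definition of a serious event includes "or a permanent impairment of a body structure or body function", which may not be possible to judge on the day of exit. Appendix G asks about yellowing of the skin or eyes and dark urine, and asks for discharge papers that exist only once hospital care has ended.

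Section 11 calls this the first study of the combination, and the synopsis says the data may be used to design a two-arm trial. An AE summary that stops at exit would be carried into that design.

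**Working it through.** **1. The plan's own figures.** Section 7.2 expects a cold in 40% of 200 enrolled: 200 x 0.40 = 80 treated, as stated. The supply in Sections 4.1 and 6.6 is 18 days x 2 packets = 36, as stated. Both reproduce.

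**2. Scheduled AE follow-up after exit, by route.**

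| Route out | Source | Scheduled AE contact afterwards |
|---|---|---|
| Symptoms resolve | 4.3, 6.2 | none |
| Day 18 reached | 4.3, 6.2 | none |
| Any medication prescribed | 4.2 | none |
| Another cold remedy taken | 4.2 | none |
| Participant leaves after an AE | 2.2.3 | none |

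The result is 0 days on every route, so the rule applies to all of about 80 treated participants. This counts people subject to the rule, not events lost.

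**3. Time from last packet to exit for a participant who resolves.** The diary comes before that day's first packet (Section 6.1). Suppose resolution is recorded in that diary, the last two packets were taken the day before, and they were 5 hours apart (the plan says 4-6). The gap is 1 - 5/24 = 0.79 day, about 19 hours.

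**4. Consistency of the forms.**
- The schedule marks AE assessment at study exit, but the exit form (Appendix F) has no AE item. The diary, also marked at exit, does.
- Diary items 10 and 11 tell a participant who took another cold remedy, or was prescribed something after seeing a doctor for the symptoms, to exit. The side-effect question is item 12, after those instructions.
- Section 6.1 describes the emailed prompt for the exit form only at resolution or after 18 days. No prompt is described for someone withdrawn earlier.

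**5. How much could be missed (illustration only).** The documents give no AE rate and no onset lag. Assume that each packet carries equal risk, onset lag after a packet is exponential with mean m days, packets are taken on days 1 to T-1 (two a day, 5 hours apart), and exit is on day T. Then

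share of onsets before exit = average over packets of [1 - exp(-(T - t)/m)], where t is the time of the packet.

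For T = 5 and m = 5, the eight packets lie 4, 3.79, 3, 2.79, 2, 1.79, 1 and 0.79 days before exit. The terms are 0.551, 0.532, 0.451, 0.428, 0.330, 0.301, 0.181 and 0.146; their sum is 2.92, and 2.92/8 = 0.365.

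| Exit day T | m = 0.5 | m = 2 | m = 5 |
|---|---|---|---|
| 5 | 95.1% | 64.8% | 36.5% |
| 8 | 97.2% | 77.5% | 50.4% |
| 11 | 98.0% | 83.8% | 60.1% |
| 18 | 98.8% | 90.4% | 73.8% |

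The loss is small for fast-onset effects. It grows with the lag and is greatest in short colds.

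**6. Precision even with complete collection.** If no event of a given type is seen in 80 treated, the one-sided 95% upper bound is 1 - 0.05^(1/80) = 3.7%. With so few participants, a handful of uncollected events would change what the summary can say.

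**The case against.** The case for leaving the plan alone has real content. The study is declared minimal risk and its ingredients are described as generally recognised as safe. The anticipated AEs in Sections 2.2.1 and 6.4.1 are mainly gastrointestinal complaints and headache, and are tied to high doses. If these start within hours, the table above puts 95% to 99% of onsets before exit. Section 6.4 provides for review by the coordinator and the investigator, reporting under the ethics board's requirements, and sponsor action under its own procedures. Nothing in Section 4.2 forbids AE reporting after withdrawal. An AE handled without a prescription or a barred cold remedy forces no exit. All of this stands, and it limits how serious the gap is.

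A reader might infer three stronger conclusions that the documents do not support:

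- **Such events are never captured.** The AE form has no stated closing date and asks for diagnosis, treatment and discharge papers. A participant can therefore report late, and some information on treated events can arrive. What is missing is planned collection.
- **The day-18 packets have no diary entry after them.** The diary precedes each day's packets, which invites this reading. But Section 6.2 marks both the diary and an AE assessment in a separate study-exit column after Days 1-18. A count of those packets would in any case not be a count of AEs.
- **The safety picture is biased towards looking benign.** That direction is plausible. It is not demonstrated: a participant withdrawn for a prescription has already reported it, the underlying AE can still be in the summary, and no rate or lag is given.

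The consent pages and any material after Appendix G were not available for this check, so post-exit reporting instructions there cannot be excluded.

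**Conclusion.** The point holds as a gap in planned collection. On the available text, scheduled AE assessment ends at exit, exit can come about 19 hours after the last packet or on the date of a prescription, and neither late onset nor final outcome has a planned route into the AE summary. All of about 80 treated participants fall under this rule.

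The number of events affected is unknown. Under the assumed lags, the share of onsets before exit runs from 99% (half-day mean lag, exit on day 18) down to 37% (five-day mean lag, exit on day 5). Nothing in the documents says where in that range the product lies. The share of participants who would be prescribed something for an AE is also not given.

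The primary analysis is unaffected. This is a worthwhile, low-cost improvement to a secondary endpoint.

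**What to change.** Separate the end of safety follow-up from the end of efficacy follow-up.

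1. **Section 6.2:** add one portal AE form after study exit, sent at a fixed short interval after the last packet to everyone who took at least one packet, including those withdrawn under Section 4.2. Seven days is an example; the interval is the sponsor's choice.
2. **Appendix G:** add a stop date, an outcome and an ongoing field.
3. **Sections 4.2 and 6.4:** reconcile them by stating that withdrawal from the product or from efficacy follow-up does not end AE data collection.

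The cost is a protocol amendment and about 80 extra electronic forms. The synopsis already expects 90 days of participation from study start, so a 7-day form falls inside that period whenever the last packet is taken by day 83 (90 - 7). For later colds it extends participation slightly. Some participants will not return the form, so the AE summary should report how many did.

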6.3. Participant Enrollment and Follow-Up

Candidates will be screened using a HIPAA-secured screening survey to determine eligibility. All eligibility criteria must be met for candidates to be approved for enrollment into the study. Candidates will be provided an informed consent form and will be given the opportunity to ask questions related to the study procedures, risks and benefits, and rights related to participation in the study. Candidates who sign the study informed consent will be prospectively enrolled in the study and provided a link to a patient portal, which provides study resources. Participants will take the test product at the onset of colds symptoms and provide information related to their cold symptoms during the follow-up period. A remote study coordinator may prompt participants to provide study information to ensure that the study forms are completed. Efforts will be taken to ensure minimal withdrawals and loss to follow-up.

6.4. Adverse Event and Safety Monitoring

Adverse Events (AEs) are defined as any untoward medical occurrences described by the study participant. All AEs will be self-reported and documented on the platform. The AEs will be reviewed by the study team including the remote trial coordinator and study principal investigator and reported according to the IRB requirements. Participants who experience adverse events will be advised to stop taking the test product and seek medical attention.

In the event that a participant experiences an adverse event, the clinical study manager or clinical ops coordinator will notify both the PI and Sponsor. The Sponsor will take appropriate action according to their standard operating procedures for any adverse events that warrant action by the sponsor.

6.4.1.Anticipated Adverse Events

Anticipated Adverse Events are complications that are known to be associated with the test product (in high doses exceeding recommended use):

- epigastric pain
- nausea
- vomiting
- loss of appetite
- abdominal cramps
- diarrhea
- headaches

6.4.2. Adverse Event Relationship

Each reported AE will be assessed by the Investigator for relatedness, severity and causality.

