The present study will be a single site, prospective, single arm observational study of minimal risk consisting of at least 200 participants who suffer from cold symptoms. The participants must meet additional inclusion/exclusion criteria (see Inclusion/Exclusion Criteria). Participants will begin taking the powder drink-mix at the onset of their cold symptoms. Onset is defined as the point in time the participant experiences 2 or more cold symptoms (cough, hoarseness, muscle ache, nasal drainage,

nasal congestion, scratchy throat, sore throat, sneezing, or an oral temperature greater than 37.7 °C (99.9 °F)). When the participant experiences 2 or more symptoms, they will report symptoms in the cold start form. If they meet the criteria for a cold, they will start completing the daily cold symptom diary prior to taking the test product. After consuming the product, the participant will complete the cold symptom diary daily until all symptoms resolve. Since none of the ingredients in the test product have been seen to provide relief from fever or pain, the participant will be allowed to take a pain reliever and fever reducer (e.g. ibuprofen or acetaminophen). If medication is taken, the participant will record this in their symptom diary.

Study enrollment and management will be decentralized, where participants do not visit an investigator or a clinic for clinical assessment. The participants will participate in the study at home. All data collected from during this study will be reported by the participant via eCRFs, eDiary, and other electronic data entries. If a visit is required, it will be conducted via remote contact by telephone.

4.1.Test Product

Overview:

Participants in this study will consume the test product twice a day (4-6 hours apart) at the onset of cold symptoms. The participant will mix one packet of the test product in 6-8 ounces of water. The test product will be delivered to the participants' residence in a single shipment consisting of an18-day supply (36 packets) of the test product. The study participant will mix the contents of the packet into 6-8 oz. of hot water and drink twice a day during the duration of the cold.

Below is the description of the test product and its ingredients.

Test Product

Description: Combining whole food sourced Vitamin C, Echinacea, Ivy Extract, Zinc, Ginger and Turmeric. This formula is designed to support the immune system while reducing the duration of cold.

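### The participant adverse event form has no structured severity, date, outcome or product-continued field and groups unlike events, so the grading required in Section 6.4.2 rests on free text and undefined follow-up

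*Combined protocol and SAP*

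**What the plan says.** Section 6.4.2 sets one duty: "Each reported AE will be assessed by the Investigator for relatedness, severity and causality". The text supplied gives no severity scale and no causality categories. Section 6.4 defines the events broadly, "Adverse Events (AEs) are defined as any untoward medical occurrences described by the study participant", and names one source, "All AEs will be self-reported and documented on the platform". Review follows: "The AEs will be reviewed by the study team including the remote trial coordinator and study principal investigator". Section 6.4.1 lists seven anticipated events, introduced by "Anticipated Adverse Events are complications that are known to be associated with the test product"; a qualifier directly after those words ties them to doses above recommended use.

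The form itself is Appendix G. It opens with a yes/no question on side effects, followed by ten named tick boxes and an Other box. Two of the boxes read "itching, rash, hives, throat/lip/tongue swelling, wheezing" and "fatigue, appetite loss, yellowing skin/eyes, itching, dark urine". The form then asks for:
- a free-text description;
- how long after taking the product the effect appeared;
- what was done to relieve it;
- whether a hospital or doctor was involved, with diagnosis, treatment and uploaded papers.

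Item 12 of the symptom diary (Appendix E) asks daily, yes or no, about side effects and sends the participant to the form. Sections 3 and 7.1 place adverse events among the secondary endpoints. Section 7.3 promises a summary but gives no counting unit and no breakdown.

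**The concern.** The investigator has to judge every event without seeing the participant in person, so the participant's entry is the main evidence. A form that does not ask how bad the event was, when it began and ended, or whether the product was still being taken leaves those facts to whatever the participant chooses to write. A tick in a shared box does not show which of several quite different events occurred.

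This matters more in a single-arm study. With no control group to give a background rate, case-by-case judgement is the only route to attribution. The illness also overlaps with the events: muscle ache is one of the cold symptoms in Section 4, and severe muscle pain is part of a box in Appendix G. Dates and severity help to separate the cold from a product effect. Facts not collected at the time may not be recoverable later.

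**Working it through.** No sample size, power or event-rate figure bears on this point, and the plan states none to reproduce. The check compares Appendix G with what Sections 6.4.1, 6.4.2 and 7.3 need from it.

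**1. Anticipated events (Section 6.4.1) against the tick boxes (Appendix G)**

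| Anticipated event | Box available |
|---|---|
| Nausea | Shared gastrointestinal box, labelled for severe and persistent events |
| Vomiting | Same box |
| Diarrhea | Same box |
| Abdominal cramps | Same box, as abdominal pain |
| Epigastric pain | Same box, as abdominal pain |
| Loss of appetite | Shared with fatigue, yellowing of skin or eyes, itching and dark urine |
| Headache | None; Other only |

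Five share one box, one sits in an unrelated box and one has no box: 5 + 1 + 1 = 7. Events with a box of their own: 0 of 7. The severity wording is read here as covering the whole gastrointestinal label. If it were meant for nausea alone, milder vomiting, diarrhea or abdominal pain would have a box, but still a shared one.

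**2. Grouping across the form**

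At least 7 of the 10 named boxes join distinct terms:
- allergic, 5 or more terms;
- cardiac and respiratory, 6;
- gastrointestinal, 4;
- urinary, 2;
- fatigue and hepatic-type, 5;
- blood in urine, stool or vomit, 3;
- mood, cognitive, behavioral and suicidal thoughts, 4.

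Itching appears in two boxes.

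**3. What the assessment needs against what is asked**

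| Needed | Structured field in Appendix G | Partial substitute |
|---|---|---|
| Severity | None | Two box labels contain the word severe; medical contact; free text |
| Calendar start date | None | Time since taking the product; daily diary item |
| Stop date | None | Repeated diary answers |
| Product continued or stopped | None | None on the forms shown |
| Outcome | None | Free text; uploaded hospital papers |
| Concomitant pain or fever medicine | None | Diary item 9 |

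**4. How far the substitutes reach**

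The question on time since taking the product does not say which packet it refers to. The text does not say whether the portal date-stamps entries. Diary item 12 can place an event roughly to a day, but repeated yes answers do not show whether it is the same event. The diary ends at symptom resolution or day 18, so a later stop date is not captured. Section 6.4 says participants with an event will be advised to stop the product, yet no form shown records whether they stopped or what followed. Section 6.2 has a schedule row for product consumption, but the diary has no item for it.

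**The case against.** The strongest reply is that Section 6.4.2 gives grading to the investigator, not the participant, so a form without a self-grade does not contradict it. The investigator has the description, timing, self-care, medical contact and uploaded records, and reading them is part of the review in Section 6.4. Contact is possible too: Section 4 says "If a visit is required, it will be conducted via remote contact by telephone", and Section 6.3 lets a coordinator prompt for study information. The diary covers side effects and pain or fever reducers daily. The shared boxes can be read as clusters of warning signs (allergic, cardiac, hepatic), in which case itching in two of them is no defect. The study is declared minimal risk, the anticipated events are linked to higher doses than those used here, and the plan promises no table by severity for the form to defeat.

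Much of this stands. A reader might infer from the form that events cannot be graded or counted separately, or that severity and timing are wholly absent. The documents do not support either: the free text and medical-care questions allow some grading and separation, and relative onset is asked.

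The forms in Appendices A to G are also not the full set. The cold start form named in Sections 4 and 6.1 is not among them, and material after Appendix G was not available for review, so an investigator-side record cannot be excluded.

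The reply does not supply the missing fields. No step to query a participant about an adverse event is written, and the telephone provision is general. If the clusters are warning signs, the form still has no separate place for the milder events that Section 6.4.1 leads one to expect.

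**Conclusion.** The point holds in a limited form. On the participant form shown, severity, calendar dates, outcome and product continuation have no structured field, at least 7 of 10 named boxes mix distinct events, and 0 of 7 anticipated events has its own box. Severity and causality assessment, and the secondary-endpoint summary, therefore rest on free text, a yes/no diary item and follow-up that is not defined. The quality of both will vary with how much each participant writes.

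This rests on three assumptions: no investigator-side form outside the text available collects these items; the portal adds no structured fields beyond Appendix G; and the severity wording covers the whole gastrointestinal label. It is not a claim that grading or separate counting is impossible, nor that the seven events are expected at the study dose. It does not touch the primary endpoint. The change is worth making because it is cheap and the missing facts may not be recoverable afterwards.

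**What to change.** In Appendix G, use one record per event, each with:
- a single event term, from a list that includes the seven anticipated events with no severity threshold in the label; existing warning signs can stay as separate terms;
- severity as mild, moderate or severe, with a short definition of each;
- start and stop dates;
- whether the product was continued;
- outcome.

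Keep the free text, medical-contact questions and document upload. Take pain and fever reducers from diary item 9 rather than asking again. In Section 7.3 or the forthcoming statistical analysis plan, state that adverse events are tabulated by event and severity, counting both participants and events.

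The cost is a portal form edit and about a minute more for a participant who reports an event. It is a change in data capture and tabulation only.
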